8.1 Subject eligibility

The investigator should only include subjects who meet all eligibility criteria, are not put at undue risk by participating in the trial, and can be expected to comply with the protocol.

The subject's eligibility for the clinical trial must be verified according to the inclusion and exclusion criteria according to the schedule of trial procedures (Section 4). It will be recorded in the eCRF if the subject has met all the inclusion criteria and none of the exclusion criteria.

Any implementation of national requirements/law for the subject's participation in the clinical trial will be ensured and described in submission documentation to regulatory authorities and IRBs/IECs, as applicable.

8.2 Inclusion criteria

The subjects must fulfil all of the following criteria to be eligible for the trial:

1. Signed and dated informed consent obtained prior to any protocol-related procedures.
2. Adult, age 18 years or older at screening.
3. Diagnosis of chronic AD as defined by the Hanifin and Rajka (1980) criteria for AD (36).
4. History of AD ≥ 1 year prior to baseline.
5. Recent (within 6 months prior to baseline) documented history of inadequate response to topical AD treatments* or subject for whom topical AD treatments are medically inadvisable.

*Inadequate response to topical AD treatments is defined as failure to achieve and maintain remission or a low disease activity state corresponding to 0 (clear) \leq IGA ≤ 2 (mild) despite treatment with a daily regimen of TCS of medium to high potency (\pm TCl, as appropriate), applied for at least 28 days or for the maximum duration recommended by the product prescribing information (e.g. 14 days for super-potent TCS).

6. $7.1 \leq$ EASI ≤ 50 at baseline.

7. vIGA-AD score ≥ 3 at baseline.
8. BSA $\geq 5\%$ at baseline.
9. Subject agrees to apply an emollient to lesional and non-lesional skin at least twice daily for at least 7 consecutive days immediately prior to baseline.
10. Women of childbearing potential* must use highly effective contraception** from randomization to the end of the trial (safety follow-up visit).

* A woman of childbearing potential is defined as a female subject aged ≥ 12 years or a younger girl who, at the discretion of the investigator, is deemed to be of reproductive potential. A woman is defined as not being of childbearing potential if she is postmenopausal (at least 12 months with no menses without an alternative medical reason prior to screening), or surgically sterile (hysterectomy, bilateral salpingectomy, or bilateral oophorectomy).

**A highly effective method of contraception is defined as one which results in a low failure rate (less than 1% per year when used correctly and consistently) such as:

- Bilateral tubal occlusion.
- IUD.
- IUS.
- Combined (estrogen- and progestogen-containing) hormonal contraception associated with inhibition of ovulation (oral, intravaginal, transdermal).
- Progestogen-only hormonal contraception associated with inhibition of ovulation (oral, injectable, implantable).
- Sexual abstinence (when this is in line with the preferred and usual lifestyle of the subject and not just being without a current partner).
- Same-sex partner.
- Vasectomized partner (given that the subject is monogamous).

8.3 Exclusion criteria

Subjects are not eligible for the trial if they violate any of the following criteria:

1. Concurrent skin disease at baseline which may interfere with the trial assessments, at the discretion of the investigator.
2. Active skin infection or any other clinically apparent infection at baseline which may interfere with the trial assessments, at the discretion of the investigator.
3. Previous treatment with an oral H4R antagonist (including LEO 152020) within 6 months prior to baseline.
4. Previous treatment with 3 or more systemic AD treatments prior to screening.
5. Systemic treatment including systemic corticosteroids known or suspected to have an effect on AD within 4 weeks or 5 half-lives prior to baseline, whichever is longer.
6. Phototherapy within 4 weeks prior to baseline.
7. Positive HBsAg, anti-HBs*, anti-HBc, or HCV serology at screening.

*Subjects with positive anti-HBs are eligible provided that they have a negative HBsAg, negative anti-HBc (blood pattern in vaccinated subjects), and negative HCV serology.

8. Current active tuberculosis based on test per local standard at screening. The screening for tuberculosis should be done according to guidelines for patients subject to biologic treatment as per local standard of care.
9. Infection with HIV.
10. History of lymphoproliferative disease or malignancy (except treated and recovered non-melanoma skin cancer or cervical carcinoma in situ) within 5 years prior to screening.

11. Subjects at risk for Torsade de Pointes based on any of the following:
 - a. Uncorrected hypokalemia or hypomagnesemia at Week -1, history of cardiac failure, history of clinically significant/symptomatic bradycardia.
 - b. **CCI** or family history of idiopathic sudden death.
12. Use within 5 half-lives prior to screening of concomitant medication for which **CCI** is a known side effect and which cannot be discontinued or replaced by (a) safe alternative medication(s).
13. Resting QTcF (average of a triplicate measurement) <300 ms or >450 ms (men) or >460 ms (women) at screening.
14. Known history of ventricular arrhythmias.
15. Second- or third degree- atrioventricular block.
16. Subjects with severe renal impairment as determined by eGFR levels below 30 mL/min at screening (37). For eGFR levels allowed in Germany and Japan, see [Appendix 4](#).
17. Subjects with medical history of chronic moderate to severe liver disease.
18. Clinically significant abnormal finding* at screening and/or baseline which, in the opinion of the investigator, may:
 - a. Affect subject safety and well-being or put the subject at risk because of their participation in the trial.
 - b. Influence the assessments.
 - c. Impede the subject's ability to complete the trial.

*Examples include clinically significant abnormal vital sign, physical examination, ECG (based on central ECG report), and laboratory result.

19. Any unstable medical, surgical, psychiatric, or additional physical disorder* at any time during the trial which, in the opinion of the investigator, may:
 - a. Affect subject safety and well-being or put the subject at risk because of their participation in the trial.
 - b. Impede the subject's ability to complete the trial.

*Examples include but are not limited to endocrine, gastrointestinal, hepatic, immunological, infectious, metabolic, musculoskeletal, neurological, and major physical impairment.

20. Known or suspected hypersensitivity to any components of the IMPs or to drugs of a similar chemical class.
21. Treatment with any nonmarketed drug substance (that is, an agent which has not yet been made available for clinical use following registration) within 4 weeks or 5 half-lives of the drug prior to baseline, whichever is longer.
22. Current participation in any other interventional clinical trial.
23. Previously screened* in this trial.

*Re-screening of subjects is not allowed unless the screening failure was due to an administrative reason (Section 8.4).
24. Current or recent chronic alcohol or drug abuse within 12 months prior to screening.
25. Subjects, who, in the opinion of the investigator, would be noncompliant or unable to understand the trial and give adequately informed consent.
26. Employees of the trial site, any other individuals directly involved with the planning or conduct of the trial, or immediate family members of such individuals.
27. Subjects who are legally institutionalized.
28. Women who are pregnant, intend to become pregnant, or are lactating.

8.4 Screening and screening failures

Subject identification number

Trial participation begins once written informed consent is obtained ([Appendix 3B](#)). Once informed consent is obtained, a subject ID will be assigned to the subject by a central IRT system.

After a subject ID has been assigned, the screening evaluations to assess eligibility may begin. The date of first screening activity can be the same as when informed consent was obtained or a later date. The subject ID will be used to identify the subject during screening and throughout the trial, if applicable. Subjects who have given written informed consent to participate in the trial and who have been assigned a subject ID are considered ‘screened’ subjects.

Investigator logs

The investigator will maintain a log of all subjects considered for screening, whether they provided written informed consent or not (screening log). This log will be anonymous and will include the allocated subject ID and the reason(s) for not entering the trial, if applicable. In addition, the investigator will maintain a log of all consented subjects (subject identification log). This log will include each subject’s identity, date of consent, and corresponding subject ID, so that any subject may be identified, if required for any reason. The log must not be copied or retained by LEO Pharma.

Screening failures

Screening failures are defined as subjects who consent to participate in the trial but who are subsequently not randomized to treatment. A minimal set of screening failure information is required to ensure transparent reporting of screening failures to meet the CONSORT publishing requirements ([38](#)) and to respond to queries from regulatory authorities. As a minimum, the following data will be recorded in the eCRF for screening failures:

- Date of informed consent(s).
- Date of screening failure.
- Reason for screening failure.
 - a. Failure to meet eligibility criteria and which eligibility criterion(ia) was (were) not met.
 - b. Withdrawal by subject.
 - c. Lost to follow-up.

d. Other (if other, a specification should be provided).

- Demographics (full date of birth [day, month, and year], only month and year, or only year as per local legislation, age, sex, race, ethnicity as per local legislation).
- Any (S)AEs.

Any SAE will require expedited reporting as described in Section [13.4](#).

Re-screening of screening failures (subjects who did not meet the eligibility criteria for participation in the trial) is not allowed. However, if the reason for screening failure is administrative and not due to the subject not meeting the eligibility criteria (e.g. delayed test results or temporary site closure due to the COVID-19 pandemic), re-screening may be permitted. This will require approval by the sponsor's medical expert after thorough review of data from the original screening visit in the eCRF. Subjects to be re-screened must sign a new ICF. Re-screened subjects will get a new subject ID. In addition, the subject ID from the previous screening will be recorded in the eCRF.

9 Treatments

9.1 Trial products description

In this trial, the IMPs are (Panel 5):

- LEO 152020 film-coated tablet 50 mg.
- LEO 152020 placebo film-coated tablet.

Panel 5: Identification of investigational medicinal products

Investigational medicinal product	Dosage form	Active ingredient and concentration	Manufacturer responsible for batch release
LEO 152020 film-coated tablet 50 mg	Film-coated tablet	CCI [REDACTED]	LEO Pharma
LEO 152020 placebo film-coated tablet	Film-coated tablet	Not applicable	LEO Pharma

CCI

Composition of LEO 152020 film-coated tablet 50 mg is described in the investigator's brochure. LEO 152020 placebo film-coated tablet contains the same ingredients as LEO 152020 film-coated tablet, except the active ingredient LEO 152020.

9.2 Administration of the investigational medicinal product

General

The IMP will be dispensed to the subject according to the schedule of trial procedures (Section 4). Dispensing of the IMP will be handled by an IRT system. At each dispensing visit, the IRT system will assign any required kit number(s) to the subject.

From baseline to Week 16, the subject will be asked to self-administer the IMP at the trial site or at their home. The subject will self-administer their first dose of IMP at the site and their last dose of IMP at home, in the evening before the Week 16 visit. At the Week 16 visit or the last visit in the trial, the investigator or site staff should confirm with the subject the date and time of last dose of IMP and record the information in the eCRF.

Every day between baseline and Week 16, the subject will be asked to take [REDACTED] tablets of IMP: [REDACTED] tablets in the CCI [REDACTED] and [REDACTED] tablets in the CCI [REDACTED] (Panel 6). Administration of the IMP will be explained to the subject in separate instructions for use in their language.

Administration of the IMP at the trial site

At the visits indicated in the schedule of trial procedures (Section 4), the subject will be asked to self-administer the IMP at the trial site under the supervision of the site staff. At baseline, the subject will self-administer the first dose of IMP at the site. At trial visits from Week 1 to Week 14, the subject will self-administer their morning dose of IMP at the site. The subject will be asked to come fasted to the trial site, i.e. arrive at the site minimum 2 hours after their last meal.

Visits should be scheduled at times to make

- Fasted state and minimum time of [REDACTED] hours between consecutive doses of IMP feasible for the subject.
- ECG measurement(s) and PK blood sampling feasible for the site staff (see Section 4 [Panel 2 and Panel 3], Sections 11.4.3 and 11.6.1).

At each visit from Week 1 to Week 14 before the subject self-administers the IMP, the site staff should check if the subject is fasted (i.e. arrived at the trial site minimum 2 hours after their last meal) and when they took their last dose of IMP and follow the flowcharts provided in Appendix 7.

Reporting in eCRF

It will be recorded in the eCRF if the subject was fasted (i.e. had arrived at the trial site minimum 2 hours after their last meal).

Administration of the IMP at the subject's home

The subject will be instructed to take [REDACTED] doses of IMP [REDACTED] hours apart and no less than [REDACTED] hours apart.

If the subject misses a dose of IMP at home

If the subject misses a dose of IMP at home, they will be instructed to proceed as follows:

- If at the time the subject becomes aware of the missed dose of IMP, there are **more** than [REDACTED] hours to the next planned dose, the subject should take the missed dose as soon as they become aware.
- If at the time the subject becomes aware of the missed dose of IMP, there are **less** than [REDACTED] hours to the next planned dose, the subject should skip the missed dose and wait until the next planned dose of IMP.

If the subject misses a visit or a dose of IMP at the trial site

If the subject misses a visit or a dose of IMP at the trial site, they will be instructed to maintain their dosing schedule and, if possible, to take the missed dose of IMP at their home instead (Panel 20).

Precautions pre- and post-dose of IMP at the trial site

ECGs will be measured pre- and/or post-dose of IMP (Section 11.4.3).

Provisions for overdose

The risk of accidental overdose with a clinical consequence is considered low as it would involve intake of an unlikely large dose of IMP at once: CCI mg in a single dose (39). This is equivalent to 1 tablets in the LEO 152020 CCI treatment group where the highest exposure is expected.

To minimize the risk of accidental overdose, site staff should explain to the subject how to self-administer the IMP and instructions for use will be given to the subject to take home. For more information about medication errors, including accidental overdose, see Section 13.6.2.

There are no available data on overdose with LEO 152020. LEO Pharma does not recommend any specific treatment in relation to overdose. It will be at the discretion of the investigator to take appropriate action to treat and follow up on any accidental overdose.

9.3 Treatment assignment and blinding

9.3.1 Treatment assignment

Subjects who comply with all eligibility criteria (Sections 8.1 to 8.3) will be randomized to 1 of the following oral treatments:

- LEO 152020 CCI
- LEO 152020 CCI
- LEO 152020 CCI
- Placebo CCI.

Within the strata defined by baseline disease severity (EASI at baseline) and region (Japan, non-Japanese countries), subjects will be randomized in a 4:3:3:4 ratio, using a permuted block design. Approximately 30% subjects with EASI between 7.1 and 16 at baseline ($7.1 \leq \text{EASI} \leq 16$) and 70% subjects with EASI between 16.1 and 50 at baseline ($16.1 \leq \text{EASI} \leq 50$) will be randomized in the trial.

The IRT system will be used to control randomization and to track stratification and IMP supply chain and expiry.

9.3.2 Blinding

Triple blinding (subject, investigator, and assessor of the data/study outcome [sponsor]) from randomization to formal unblinding of the trial will be applied.

Investigational medicinal product

The packaging and labelling of the IMPs will contain no evidence of their identity. LEO 152020 film-coated tablets 50 mg and LEO 152020 placebo film-coated tablets have been designed to look alike (same size and color) and telling them apart by sensory evaluation is not considered possible.

To ensure blinding across all treatment groups, subjects will be asked to take \blacksquare tablets of IMP daily: \blacksquare tablets in the **CCI** and \blacksquare tablets in the **CCI** (Section 9.2) as described in Panel 6.

Panel 6: Dosing schedule and treatment composition in each treatment group

Treatment group	CCI dose of IMP		CCI dose of IMP	
	LEO 152020 film-coated tablet 50 mg	LEO 152020 placebo film-coated tablet	LEO 152020 film-coated tablet 50 mg	LEO 152020 placebo film-coated tablet
LEO 152020 CCI	CCI			
LEO 152020 CCI				
LEO 152020 CCI				
Placebo CCI				

Abbreviations: IMP = investigational medicinal product.

To avoid medication errors in the LEO 152020 CCI treatment group and to ensure blinding across all treatment groups, the CCI doses of IMP must clearly be identified on the packaging for all treatment groups. Packaging and labelling of the IMPs is described in more detail in Section 9.8.1.

Safety

During trial conduct, unblinding of an individual subject for emergency or regulatory purposes (SUSAR reporting) may be necessary. In such cases, unblinding will strictly be limited to the individual(s) needed to conduct the unblinding procedure. No unblinded safety data will be shared with the rest of the clinical team before DBL. For more information about emergency unblinding, see Section 9.3.3.

Subject safety and overall trial conduct will be monitored by an external unblinded DMC not involved in trial conduct as described in a separate DMC charter (see also Appendix 3H). In their interactions with the sponsor, the DMC will not share unblinded data.

Pharmacokinetics and pharmacodynamics

PK and PD samples will be collected for all subjects as part of the general blood work in the trial. Skin biopsies are an optional component of the trial and will be collected for a subgroup of subjects randomly and without knowledge of treatment allocation (Section 11.7.3).

PK blood samples of subjects treated with LEO 152020 will be analyzed by an external unblinded, specialized laboratory not involved in trial conduct. During the trial, raw PK data will be reviewed by an unblinded monitoring scientist at the sponsor to ensure data quality. In this context, unblinding means knowing the link between subject ID and treatment allocation only. No unblinded PK data will be shared with the clinical team at the sponsor before DBL.

All PD blood samples and skin biopsies will be analyzed by an external unblinded, specialized laboratory not involved in trial conduct. No unblinded PD data will be shared with the sponsor clinical team before DBL.

Data monitoring

Until DBL, data monitoring at the sponsor will be conducted on blinded data.

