To evaluate effect of treatment with LEO 152020 compared with placebo for up to 16 weeks of treatment on PROs in subjects with moderate to severe AD	Exploratory endpoints 
 Change in POEM from baseline to Week 16. Change in DLQI from baseline to Week 16. Having a decrease in DLQI of at least 4 points from baseline to Week 16 in subjects with DLQI ≥ 4 at baseline. Change in EQ-5D-5L from baseline to Week 16. Change in HADS from baseline to Week 16. Change in WPAI:AD (for each individual domain) from baseline to Week 16. Having a decrease in POEM of at least 4 points from baseline to Week 16 in subjects with POEM ≥ 4 at baseline.
Exploratory objectives (continued)	
To evaluate pharmacokinetic parameters of LEO 152020 for up to 16 weeks of treatment in subjects with moderate to severe AD	Exploratory endpoint 
 C_{trough} of LEO 152020 at Weeks CCI . C_{max} of LEO 152020 at Weeks CCI .

Objectives	Endpoints

To evaluate effect of treatment with LEO 152020 compared with placebo for [CCI] of treatment on disease biomarkers and biomarkers related to the mechanism of action of LEO 152020 in subjects with moderate to severe AD
	
Exploratory endpoints
 
 • Change in expression levels of blood biomarkers from baseline to [CCI] • Change in expression levels of AD disease biomarkers in skin from baseline to [CCI]

To explore the effect of treatment with LEO 152020 compared with placebo for [CCI] of treatment on sleep disturbance and nocturnal [CCI] in subjects with moderate to severe AD
	
Exploratory endpoints
 
Based on eDiary data
 
 • Difficulty [CCI] at Week [CCI] • Frequency of [CCI] During the Night at Week [CCI] • [CCI] at Week [CCI] • [CCI] at Week [CCI] 
Based on actigraphy data
 
 • Change in [CCI] from baseline to Week [CCI] • Change in [CCI] from baseline to Week [CCI] • Change in number of nocturnal [CCI] events per hour from baseline to Week [CCI] • Change in duration of nocturnal [CCI] per hour from baseline to Week [CCI]

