11.10 Storage of biological samples

The blood and urine samples for laboratory testing (clinical chemistry, hematology, serology, and urinalysis) will be collected to monitor and ensure subject safety during the trial and will only be stored until analysis is completed by the central laboratory.

PK blood samples will be retained for as long as the quality of the material permits evaluation but for no longer than 12 months after completion of the CTR. Any remaining PK samples may be used for semi-quantitative metabolite identification.

PD blood samples and skin biopsies will be retained for as long as the quality of the material permits evaluation but for no longer than 12 months after completion of the CTR. If the subject provides additional consent for this, the residual material from PD blood samples and skin biopsies will be transferred to a biobank established by LEO Pharma and hosted by **CCI** (Germany). The residual samples will be used for future research conducted by LEO Pharma. The samples will be labelled with the trial ID, subject ID, and sample date to protect subject privacy and allow for continued blinding in future analyses. The samples will be stored in the biobank for as long as the quality of the material permits evaluation and will then be destroyed.

12 Scientific rationale for trial design and appropriateness of assessments

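### Section 9.3.2 sends all PD blood samples and skin biopsies to an unblinded laboratory without saying why, which leaves an avoidable risk of differential handling in the exploratory biomarker comparisons

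*Combined protocol and SAP*

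**What the plan says.** Section 9.3.2 (Blinding) opens with the declared level of blinding: "Triple blinding (subject, investigator, and assessor of the data/study outcome [sponsor]) from randomization to formal unblinding of the trial will be applied". Its part on pharmacokinetics and pharmacodynamics then covers two laboratories.

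- **Collection.** "PK and PD samples will be collected for all subjects as part of the general blood work in the trial". Skin biopsies are optional and are to be taken from a subgroup without knowledge of treatment.
- **PK laboratory.** "PK blood samples of subjects treated with LEO 152020 will be analyzed by an external unblinded, specialized laboratory not involved in trial conduct". An unblinded monitoring scientist at the sponsor also reviews raw PK data, and the text adds: "In this context, unblinding means knowing the link between subject ID and treatment allocation only".
- **PD laboratory.** "All PD blood samples and skin biopsies will be analyzed by an external unblinded, specialized laboratory not involved in trial conduct". The accompanying safeguard is: "No unblinded PD data will be shared with the sponsor clinical team before DBL".

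These samples feed both biomarker endpoints in Section 6 (Panel 4), one in blood and one in skin. Both are exploratory and both compare LEO 152020 with placebo.

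**The concern.** A laboratory that knows the treatment arm can, without intending to, treat samples differently by arm. Serum assays and gene expression are read by instruments, but people still decide which samples to reject, which runs to repeat, which values to treat as outliers, how to form batches, and which biopsies fail a quality check. If such decisions are made with the arm in view, a difference between active treatment and placebo may partly reflect handling.

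The ordinary protection is to keep allocation from the laboratory unless it is needed there. The protocol withholds that protection for PD samples and does not say why.

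What is at stake is the credibility of the molecular evidence. Section 12.2 (Appropriateness of assessments) intends the biopsies to show resolution of disease at the molecular level and to search for markers that predict response. Efficacy on EASI is not at stake.

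**Working it through.** No power, alpha or sample-size figure bears on this point, so there is nothing to reproduce. The check is a comparison of the provisions.

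1. **Is allocation needed to select samples?**
   - For PK, Sections 9.3.2 and 11.6.1 limit the assay to subjects treated with LEO 152020, so someone must identify those subjects.
   - For PD, Section 9.3.2 collects blood from all subjects and sends all PD blood samples and biopsies to the laboratory. No selection by arm takes place.

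2. **Is another reason stated?** The relevant places are Sections 9.3.2, 11.6.2 (Pharmacodynamic assessments), 11.7.3 (Skin biopsies), 11.10 (Storage of biological samples), 12.2 and 14.3.12 (Analysis of pharmacodynamics). None gives a reason for unblinding the PD laboratory.

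3. **What do the stated safeguards protect?**
   - The laboratory is external and not involved in trial conduct. This protects the conduct of visits and assessments.
   - No unblinded PD data reach the sponsor clinical team before database lock. This protects the sponsor's blind.
   - The biopsies are collected without knowledge of treatment. This protects collection.
   - None of these acts on the assay. The sections above describe no coded assay, blinded quality control or blinded repeat rule.

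4. **Does the declared blinding cover the laboratory?** It does not. Section 9.3.2 identifies the assessor of the outcome with the sponsor.

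5. **Is coded handling feasible?** Section 11.10 labels residual PD blood and biopsy material for the biobank with trial ID, subject ID and sample date, partly to protect privacy and partly to "allow for continued blinding in future analyses". This concerns residual material only, but it shows that the sponsor can handle such samples under code.

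6. **How much is affected?** PD blood is planned for all 224 subjects. Biopsies are planned for up to approximately 40% of randomized subjects (Section 11.7.3): 0.40 × 224 = 89.6, so about 90 subjects. The documents give no assay variance, repeat rule or expected biomarker effect, so the size of any distortion cannot be calculated.

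**The case against.** The strongest reply is that the laboratory may need allocation for reasons the protocol leaves unstated.

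- Section 11.6.2 allows the blood biomarker analysis to be skipped if no superiority over placebo is seen, so that decision depends on the comparative result.
- Section 14.3.12 allows analysis to be dropped for a treatment group with biopsies from fewer than 10% of its randomized subjects, which requires counts by arm.
- Allocation can also be used to balance arms across assay batches.

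These provisions are real, but none requires the people running the assay to know each subject's arm. Someone outside the assay can decide whether to run it, apply the 10% rule, or supply a balanced batch list without treatment labels.

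A second reply is that the word unblinded is not defined for the PD laboratory. The definition quoted above sits in the PK paragraph and is not repeated, and a laboratory manual outside these documents may require coding. This stands as a limit on certainty: when and in what form the laboratory receives allocation is not stated. If the manual does require coding, the wording of Section 9.3.2 is wrong and still needs correcting.

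Three stronger readings are tempting, and the documents do not support them.

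- A reader might infer that bias is built into every biomarker endpoint. The text shows an unprotected step. It contains nothing on plate layout, repeats or exclusions that shows differential handling.
- A reader might infer a contradiction with the triple-blind label. There is none, because that label covers subject, investigator and sponsor only.
- A reader might take Section 11.10 as evidence that the trial's own PD samples are already coded for a blinded assay. The section addresses only residual material stored with additional consent. A subject ID also does not blind a laboratory that holds the link to treatment.

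**Conclusion.** The point holds as an avoidable risk in the exploratory part of the trial. The PD laboratory is described as unblinded, the PK reason does not apply to it, no other reason is given, and no stated safeguard protects the measurement.

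Its weight is low. Section 11.6.2 calls the biomarker assessments exploratory, and Section 14.3.7 (Testing strategy) confines the gatekeeping procedure to change in EASI. The primary analysis and its type I error are therefore untouched. The blood analysis may not be carried out, and the skin analysis may be dropped for a sparsely sampled group.

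The conclusion assumes that unblinded carries its plain meaning for the PD laboratory, namely access to the link between subject and treatment. It also assumes that no laboratory document already withholds that link. Confidence is high on what the text says and lower on its practical effect, which cannot be quantified.

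**What to change.** Amend the PD paragraph of Section 9.3.2 so that:

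- PD blood samples and skin biopsies are assayed and quality-controlled under subject and sample IDs, without treatment allocation;
- allocation is merged only after the PD data have been transferred and locked;
- the unblinded provision remains for PK only;
- any decision that depends on allocation (the conditions in Sections 11.6.2 and 14.3.12, or the balancing of batches) is made by someone outside the assay.

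If there is a genuine need for the PD laboratory to know allocation, Section 9.3.2 should state that need and say what prevents differential handling.

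The cost should be small: a short change to Section 9.3.2, plus alignment of the laboratory manual and data-transfer instructions. That is a judgement, since the laboratory's contract and procedures are not in the documents. The change alters no endpoint, sample size or analysis model.
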